## **11.5 Safety and Tolerability Assessments**

### **11.5.1 Adverse Events**

A baseline sign and symptom is defined as an AE that starts after the subject has provided written informed consent and that resolves prior to the first dosing occasion, or an AE that starts prior to the first dosing occasion and does not increase in severity after dosing. A treatment-emergent AE (TEAE) is defined as an AE that occurs postdose or that is present predose and becomes more severe postdose. If the start date of an AE is incomplete or missing, it will be assumed to be a TEAE, except if the incomplete start date or the stop date indicates that the event started prior to the first dosing.

AEs occurring during administration of the Period 1 Day 1 dose up to the dose administration in Period 2 Day 1 will be assigned to Period 1. Any AEs occurring during administration of the Period 2 Day 1 dose and postdose from Period 2 Day 1 to Follow-up will be assigned to Period 2.

All AEs will be listed. The TEAEs will be summarized by treatment, severity rated based on National Cancer Institute Common Terminology Criteria for Adverse Events, and relationship to the study drug. The frequency (the number of TEAEs, the number of subjects experiencing a TEAE, and the percentage of subjects experiencing a TEAE) of TEAEs will be summarized by treatment, and by Medical Dictionary for Regulatory Activities system organ class and preferred term. The summary and frequency TEAE tables will be presented for all causalities and for those TEAEs considered related to the study drug (those that have a relationship of suspected). Any TEAEs with NCI CTCAE  $\geq$  Grade 3 or serious AEs or any AEs of special interest (AESIs) or deaths will be tabulated. For any AEs that change severity ratings the AE will be included only once under the maximum severity rating in the summaries.

### **11.5.2 Clinical Laboratory Parameters**

All chemistry, hematology, and urinalysis data outside the clinical reference ranges will be listed by parameter and treatment.

All other laboratory assessments not detailed in this section will be listed but not summarized or statistically analyzed.

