3.4 SECONDARY ENDPOINTS

The secondary endpoints are:

- Incidence and severity of AEs and incidence of abnormalities in laboratory safety tests, 12-lead ECGs, and vital sign measurements.

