## 6 STUDY ENDPOINTS

The primary endpoints are:

- The geometric mean ratios and associated 90% confidence intervals (CIs) of entrectinib and M5 metabolite PK parameters area under the concentration-time curve (AUC) extrapolated to infinity ( $AUC_{0-\infty}$ ) and maximum observed concentration ( $C_{max}$ ).

The secondary endpoints are:

- Incidence and severity of adverse events (AEs) and incidence of abnormalities in laboratory safety tests, 12-lead electrocardiograms (ECGs) and vital sign measurements.

[figure not shown]

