### **11.1.2 Repeat and Unscheduled Readings**

Repeat readings occur when the original vital signs or ECG result requires confirmation. Repeat readings are labelled as ‘Repeat’ in the listings and replace the original readings in all summaries and changes from baseline presentations and calculations. Prior to dosing, all readings taken in addition to the original reading are defined as predose repeats. Postdose repeat readings are defined as readings collected within 15 minutes of the actual time of the original reading.

With the exception of predose results described above, unscheduled readings for vital signs or ECGs are defined as readings collected >15 minutes from the actual time of the original reading. Unscheduled readings are labelled as ‘Unscheduled’ in the listings. Because unscheduled readings are not associated with any scheduled timepoint, they are excluded from all summaries (with the exception that they may be used as baseline, as stated in [Section 11.1.1](#)).

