### **11.5.3 Vital Signs**

Vital signs values outside the clinical reference ranges will be flagged on the individual subject data listings.

The vital signs data will be summarized by treatment, together with changes from baseline. Figures of mean vital signs and mean change from baseline profiles will be presented by treatment.

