#### **11.5.4 Electrocardiogram**

The ECG data will be obtained directly from the 12-lead ECG traces. These data include the QT interval calculated using the Bazett correction (QTcB), the QT interval calculated using the Fridericia correction (QTcF), the PR and QT intervals, the QRS duration, and heart rate.

Values for ECG parameters outside the clinical reference ranges will be flagged on the individual subject data listings.

The ECG data will be summarized by treatment, together with changes from baseline. Figures of mean ECG data and mean change from baseline profiles will be presented by treatment.

An outlier analysis will be performed including all individual postdose measurements (not the mean data), including all repeat and unscheduled readings. The frequency of subjects with a maximum increase from baseline in QTcF intervals will be summarized for each treatment according to the following categories: >30, >60, and ≤30 ms. All incidences of >30 and >60 ms will be flagged on the listing. In addition, the frequency of subjects with QTcF postdose values will be summarized for each treatment, according to the following categories: >450, >480, >500, and ≤450 ms. All incidences of >450, >480, and >500 ms will be flagged on the listing.

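### Does the SAP leave the incidence of laboratory, ECG and vital-sign abnormalities, a named secondary endpoint, without a definition or a count?

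*SAP*

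**What the plan says.** Protocol 3.4 sets out a secondary endpoint with two parts: the incidence and severity of adverse events, and the "incidence of abnormalities in laboratory safety tests, 12-lead ECGs, and vital sign measurements". SAP 6 repeats the second part as "incidence of abnormalities in laboratory safety tests, 12-lead electrocardiograms (ECGs) and vital sign measurements".

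The analysis text then treats the three domains as follows.

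- **Laboratory (SAP 11.5.2):** "All chemistry, hematology, and urinalysis data outside the clinical reference ranges will be listed by parameter and treatment". No subject count is mentioned.
- **Vital signs (SAP 11.5.3):** "Vital signs values outside the clinical reference ranges will be flagged on the individual subject data listings". In addition, "The vital signs data will be summarized by treatment, together with changes from baseline".
- **ECG (SAP 11.5.4):** out-of-range values are flagged in the same way, and "The ECG data will be summarized by treatment, together with changes from baseline". There is also an outlier analysis. Subjects are counted by treatment according to their largest QTcF increase (above 30 and above 60 ms), and "the frequency of subjects with QTcF postdose values will be summarized for each treatment, according to the following categories" above 450, 480 and 500 ms. That analysis uses all repeat and unscheduled readings.

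SAP 11.1.2 says that repeat vital-sign and ECG readings "replace the original readings in all summaries and changes from baseline presentations and calculations". Unscheduled readings are left out of the summaries, apart from possible use as baseline, but both kinds stay labelled in the listings. SAP 4 leaves the detailed description of tables and listings to a separate shell document. SAP 11.5.6 plans no inferential safety analysis.

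**The concern.** An incidence needs a definition of the event, a counting unit and a denominator. The QTcF paragraph of SAP 11.5.4 gives all of these. Laboratory tests, vital signs and the other ECG intervals have none of them written out. Summaries of values do not fill the gap, because a mean, minimum and maximum at each timepoint do not show how many different subjects were abnormal. The adverse event tables do not fill it either, since Protocol 8.3.1.4 and 8.3.1.5 state that only some abnormal laboratory and vital-sign values count as adverse events.

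The definition is not trivial. Inclusion criterion 4 in Protocol 5.3 admits subjects whose laboratory values are out of range but judged unimportant. An abnormality could therefore mean any out-of-range value, one that is newly out of range, or one that is clinically significant. If the choice were left until after the data were seen, part of a named secondary endpoint would be reported under a rule fitted to the results.

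**Working it through.** The plan states no figure on this point, so there is nothing to reproduce. The check compares the sections and then asks how much an explicit count would add.

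**1. Is there a criterion?** SAP 11.5.2, 11.5.3 and 11.5.4 all select or flag values by the same test, whether the value lies beyond the clinical reference range. QTcF has explicit cut-offs as well. What is missing is a sentence tying this criterion to the endpoint in SAP 6.

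**2. Does each plausible reading have an output?**

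| Reading of abnormality | Where it appears |
|---|---|
| Clinically significant laboratory or vital-sign result | Reportable as an adverse event under Protocol 8.3.1.4 and 8.3.1.5; SAP 11.5.1 then gives the number and percentage of subjects by treatment and preferred term |
| Any out-of-range laboratory value | Listed by parameter and treatment (SAP 11.5.2) |
| Any out-of-range vital-sign or ECG value | Flagged on the subject listings (SAP 11.5.3, 11.5.4) |
| QTcF beyond a threshold | Subject frequency by treatment (SAP 11.5.4) |

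There are two limits to the first row. A result that is a sign of a disease is recorded under the diagnosis, and Protocol 8.3.1 has no parallel section for ECGs. For ECGs, the general definition in Protocol 8.1.1 covers deteriorations that cause symptoms or lead to a change in treatment, and Protocol 8.1.3 names QT prolongation of Grade 2 or higher as an event of special interest.

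**3. Can subjects be counted from the listings?** Protocol Appendix B gives 5 chemistry and 5 CBC samples per subject, which matches Table 7-1: 1 Screening + 2 Check-ins + 2 Discharges. That leaves one scheduled postdose draw per period, or 14 × 2 = 28 in the study. For a given parameter and treatment, the number of postdose lines in the listing is then almost directly the number of subjects.

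Table 7-1 marks three postdose timepoints per period for vital signs and ECGs, or 14 × 2 × 3 = 84 sets of readings. Suppose one value is out of range at each of the three timepoints under one treatment. The by-timepoint N, mean, SD, median, minimum and maximum can be identical in two quite different cases:

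- the same subject each time: 1/14 = 7.1%, exact 95% interval 0.2 to 33.9%;
- three different subjects: 3/14 = 21.4%, exact 95% interval 4.7 to 50.8%.

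The summaries cannot tell these apart. The flagged subject listings do so at a glance, and repeat and unscheduled readings are labelled there.

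**4. What would a formal count be worth?** For zero events in n subjects the upper exact 95% limit is 1 − 0.025^(1/n). This gives 23.2% for n = 14 and 26.5% for n = 12.

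Protocol Appendix A lists 17 chemistry and 14 blood-count measurements, 31 in all. Assume that each has probability p of lying out of range by chance and that all are independent. The documents give neither assumption. The chance of at least one out-of-range result at a single draw is 1 − (1 − p)^31:

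- p = 0.01: 1 − 0.99^31 = 0.268
- p = 0.025: 1 − 0.975^31 = 0.544
- p = 0.05: 1 − 0.95^31 = 0.796

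Per parameter, the expected chance count among 14 subjects is 14 × 0.01 = 0.14 to 14 × 0.05 = 0.7. Independence is doubtful, because hemoglobin, hematocrit and the red-cell indices move together. Subjects are also screened on these same tests. The range shows only that the definition can matter, and that under the loosest one most of the count would be noise.

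**The case for a change.** The strongest opposing case is that the endpoint is named in both documents and the SAP should deliver it. The QTcF paragraph shows that the authors knew how to specify a subject frequency, and SAP 11.5.5 sends whatever is not detailed to listings. The rule in SAP 11.1 for counts and percentages of categorical data does not help, because no normal/abnormal category is defined. With a chance-only range of 27% to 80% for at least one out-of-range laboratory value, the reported figure depends heavily on the rule. Writing the rule down costs a few lines.

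The factual part of this stands. Apart from QTcF and adverse events, the SAP text specifies listings and flags, with no subject counts, and it never states what an abnormality is for this endpoint. Two further steps do not stand. It cannot be said that the rule would be chosen after the data are seen: SAP 4 requires the SAP to be final before database lock and places table detail in the shells, so an incidence table may already be planned. Nor does the absence of a count from the text lead to a wrong result, since every out-of-range value is displayed by subject.

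A side issue is whether laboratory values get descriptive summaries. Protocol 9.5 plans descriptive statistics for the safety parameters, SAP 11.5.2 mentions only listings, and SAP 13 reports no changes. That concerns how values are presented and does not bear on the incidence of abnormalities.

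**Conclusion.** The observation about the text is right, but it calls for no change to the plan. The working definition is already in use across the three sections, clinically significant laboratory and vital-sign findings are counted through the adverse event tables, QTcF has its own frequencies, and the rest can be counted from listings in a study of 14 healthy subjects. An analyst following the SAP would produce sound descriptive safety results and no wrong number.

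The stake is small. The objective is to explore safety and tolerability, no inference is planned, and a count out of 12 or 14 carries an upper 95% limit of 23% to 27% even when no event is seen. The primary comparison of AUC and Cmax is unaffected.

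This rests on three assumptions: the listings identify subject and timepoint, as Protocol 9.1 says; the reference-range criterion is applied consistently across treatments; and the investigator records clinically significant laboratory and vital-sign results as adverse events, as Protocol 8.3.1.4 and 8.3.1.5 require. The table shells were not available, so whether they already contain an incidence table remains open. The conclusion does not depend on it.

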Duration of Treatment:	Planned Enrollment/Screening Duration: approximately 4 weeks. Length of Each Confinement: Subjects will be confined at the study site from the time of Check-in (Day -1) of each period until Clinic Discharge on Day 5. There will be at least a 14-day washout between doses in Periods 1 and 2. There will be a follow-up telephone call 12 to 14 days after the last dose of study drug (Period 2). Planned Study Conduct Duration: approximately 8 weeks.
Criteria for Evaluation: Safety	Safety and tolerability assessments will include recording of adverse events, clinical laboratory evaluations, vital sign measurements, physical examinations, and ECGs.
Criteria for Evaluation: Pharmacokinetics	The following pharmacokinetic (PK) parameters will be derived from the plasma concentrations of entrectinib and M5 using the model independent approach: maximum observed concentration (C _{max}), time to maximum observed concentration (t _{max}), area under the concentration-time curve (AUC) from Hour 0 to the last measurable concentration (AUC _{0-t}), AUC extrapolated to infinity (AUC _{0-∞}), apparent terminal elimination rate constant (λ _z), apparent terminal elimination half-life (t _{1/2}), apparent systemic clearance (entrectinib only, CL/F), and apparent volume of distribution during the terminal elimination phase (entrectinib only, V _z /F).
Statistical Methods:	Descriptive statistics (mean, median, minimum, maximum, standard deviation, geometric mean, and geometric coefficient of variation) will be calculated for all PK parameters and PK concentration data. The primary parameters for analysis will be C _{max} and AUC _{0-∞} of entrectinib and M5. A

	
linear mixed model will be applied to analyze the log-transformed primary PK parameters. The model assumes fixed effects for treatment, period, and sequence, and a random effect for subject within sequence. Estimates of geometric mean ratios on the original scale, together with the corresponding 90% confidence intervals (CIs), will be derived for the comparisons between Test and Reference treatments.
 
Descriptive statistics will be calculated on the safety parameters. No formal statistical analyses are planned.

--	---

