9.1 SAFETY AND TOLERABILITY ANALYSIS

Safety will be assessed by a review of AEs, vital signs, clinical laboratory assessments, and ECGs. Clinical laboratory assessments, vital signs (including oral temperature, respiratory rate, and supine blood pressure and pulse rate), and ECGs will be listed by subject number and scheduled time. Changes from baseline will be summarized, as appropriate.

Verbatim descriptions of AEs will be coded according to current Medical Dictionary for Regulatory Activities version 21.1 (or higher) guidelines. Adverse events will be summarized.

Enrollment and discontinuations from the study will be summarized overall. Demographics and baseline characteristics such as age, sex, and BMI will be summarized overall.

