9.5 STATISTICAL ANALYSES OF SAFETY DATA

Descriptive statistics will be calculated for the safety parameters. No formal statistical analyses are planned.

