#### 11.1.1 Definition of Baseline and Change from Baseline

Period specific baseline for each parameter is defined as the last value measured prior to dosing in each period, including repeat (vital signs and ECGs) and unscheduled (clinical laboratory parameters) readings (see [Section 11.1.2](#) for definitions of repeat and unscheduled readings).

Mean change from period specific baseline is the mean of all individual subjects' change from baseline values. Each individual change from baseline will be calculated by subtracting the individual subject's baseline value from the value at the timepoint. The individual subject's change from baseline values will be used to calculate the mean change from baseline using a SAS procedure such as Proc Univariate.

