### **13 CHANGES FROM THE PROTOCOL SPECIFIED STATISTICAL ANALYSES**

There were no changes from the protocol-specified statistical analyses.

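### SAP 11.5.2 names only an out-of-range listing for chemistry, hematology and urinalysis, although the protocol plans descriptive statistics for the safety parameters and SAP 13 declares no change

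*SAP*

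**What the plan says.** **Protocol.** Section 9.1 names clinical laboratory assessments among the data used to assess safety. Its listing sentence covers laboratory assessments, vital signs and ECGs together and ends "ECGs will be listed by subject number and scheduled time". The next sentence reads "Changes from baseline will be summarized, as appropriate". Section 9.5 is unqualified: "Descriptive statistics will be calculated for the safety parameters". The synopsis agrees: "Descriptive statistics will be calculated on the safety parameters".

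**SAP.** For the main laboratory panels, Section 11.5.2 says "All chemistry, hematology, and urinalysis data outside the clinical reference ranges will be listed by parameter and treatment". Its only other sentence says that remaining laboratory assessments are listed without summary. For vital signs, Section 11.5.3 says "The vital signs data will be summarized by treatment, together with changes from baseline", and Section 11.5.4 makes the same provision for ECGs. The period-specific baseline in Section 11.1.1 is the last value before dosing, "including repeat (vital signs and ECGs) and unscheduled (clinical laboratory parameters) readings", so it covers laboratory data. Section 4 lets the SAP supersede the protocol's statistical section on condition that substantial differences are identified. Section 13 states "There were no changes from the protocol-specified statistical analyses".

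**The concern.** The protocol treats three kinds of safety data alike, and the SAP carries the summaries forward for two of them. For the third it names only a listing of abnormal values, without giving a reason or declaring a change. A reader who relies on SAP 13 would believe that the protocol's descriptive statistics for laboratory data are still planned.

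Safety and tolerability of each formulation is the secondary objective. Inclusion criterion 4 admits subjects whose laboratory values are in range or judged not clinically significant, so a modest effect of a dose would mostly leave values in range. A listing restricted to out-of-range values would not describe such an effect or set the two formulations side by side. The protocol gives some reason to look: liver and hemolymphopoietic findings in animals (2.1.2), and raised creatinine (14%) and anemia (11%) among treatment-related events in patients (2.1.4).

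**Working it through.** **1. Comparison of the texts.** The documents give no figure to reproduce on this point, so the finding rests on the wording.

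| Data | Protocol 9.1 and 9.5 | SAP output named |
|---|---|---|
| Vital signs | Full listing; descriptive statistics; change from baseline where appropriate | By-treatment summary and change from baseline (11.5.3) |
| ECG | Same | By-treatment summary and change from baseline (11.5.4) |
| Chemistry, hematology, urinalysis | Same | Listing of out-of-range values (11.5.2) |

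The laboratory row is the only one that loses its summary. The laboratory part of the baseline definition in SAP 11.1.1 then has no named output to serve.

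**2. Data available.** Protocol Table 7-1 schedules chemistry, CBC and urinalysis at screening, at Day -1 of each period, and at 96 h or discharge of each period. That is 1 + 2 × 2 = 5 draws, which agrees with the five chemistry and five CBC samples in Appendix B. Each subject who completes both periods therefore gives one baseline-to-96 h pair per formulation: up to 14 pairs with 14 enrolled, 12 if only the planned minimum completes.

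**3. Illustration of size.** These assumptions are not in the documents: normally distributed values, a reference range of mean ± 1.96 between-subject SD, a uniform upward shift of 0.5 SD under one formulation, and a within-subject correlation r of 0.6 to 0.8.

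*What an out-of-range listing would show (n = 14).*
- High values: P(Z > 1.96) = 0.025 without the shift and P(Z > 1.46) = 0.072 with it. Expected numbers are 14 × 0.025 = 0.35 and 14 × 0.072 = 1.0.
- Probability of no high value despite the shift: (1 − 0.072)^14 = 0.35.
- Both tails together: the expected number out of range rises from 0.70 to 1.11, and the probability of none is 0.32.

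*What a mean change would show.* In between-subject SD units, SD of change = √(2(1 − r)) and SE = SD/√n.

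| r | SD of change | SE, n = 14 | 0.5/SE, n = 14 | SE, n = 12 | 0.5/SE, n = 12 |
|---|---|---|---|---|---|
| 0.6 | 0.89 | 0.24 | 2.1 | 0.26 | 1.9 |
| 0.8 | 0.63 | 0.17 | 3.0 | 0.18 | 2.7 |

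*Limits of the illustration.*
- It concerns one analyte within one formulation. If only one formulation shifts the analyte and the two changes are independent, the SE of their difference is √2 larger. At n = 14 the signal is then 2.1/√2 = 1.5 to 3.0/√2 = 2.1 SE.
- Appendix A lists 17 chemistry and, counting the five differential cells, 14 CBC parameters. Two formulations give 2 × 31 = 62 mean changes, of which 62 × 0.05 = 3.1 would pass a two-sided 5% threshold by chance. The summaries describe; they do not test.

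**The case against.** The strongest reply has five parts.

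*The protocol left room for judgement.* The change-from-baseline sentence in Protocol 9.1 is qualified, so limiting those summaries to vital signs and ECGs could fall within it. This stands, and it would be wrong to infer that the protocol guaranteed laboratory change from baseline. But the descriptive-statistics commitment in 9.5 and the synopsis carries no such qualifier. The SAP also nowhere says that laboratory summaries were judged inappropriate.

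*Other outputs may exist.* A reader might infer that an in-range shift could not be seen at all. The documents do not support that. SAP 11.1 provides general data listings, SAP 4 puts the detailed outputs in table shells that were not supplied, and SAP 11.5.2 does not say that its listing is the only output. Because that section expressly rules out summaries only for the other laboratory assessments, summaries of the main panels may even have been intended. What stands is narrower: no such summary is named in the SAP, and a listing of individual values is not the descriptive statistics promised.

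*Mean level is not the endpoint.* The laboratory endpoint is incidence of abnormalities, for which out-of-range values are the raw material. Clinically significant laboratory changes are also recorded as adverse events and summarized by treatment. This stands and limits the weight of the point.

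*A signal is unlikely.* The animal findings were dose- and exposure-dependent, and the creatinine and anemia figures come from oncology patients. Single doses up to 800 mg in healthy volunteers gave no significant safety findings (2.1.4). The only scheduled postdose draw is at 96 h, which is 96/30 = 3.2 to 96/20 = 4.8 entrectinib half-lives after dosing. This is fair, and the point does not rest on expecting an effect.

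*The size is assumed.* Neither the shift nor the correlations come from the documents, and the advantage shrinks with 12 subjects, between formulations and across many analytes. The figures are therefore illustrative only.

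**Conclusion.** The discrepancy holds as a mismatch between SAP and protocol in a descriptive secondary safety output. SAP 11.5.2 names no by-treatment summary for chemistry, hematology or urinalysis, although Protocol 9.5 and the synopsis promise descriptive statistics for the safety parameters. The laboratory baseline goes unused by any laboratory output that the SAP names, and SAP 13 reports no change.

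The consequence is modest. Up to 14 baseline-to-96 h pairs per formulation (12 at the planned minimum) have no named summary. Under the stated assumptions, a 0.5 SD shift would add well under one expected out-of-range value among 14 subjects, whereas the mean change would be about 2 to 3 standard errors for one analyte within one formulation.

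The documents support neither a claim that laboratory effects would be hidden nor one that the trial's main result is at risk. The laboratory data are collected, individual values may be listed elsewhere, and the primary pharmacokinetic analysis does not depend on them.

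**What to change.** Amend SAP 11.5.2 to:
- summarize the continuous chemistry and hematology parameters by treatment at Day -1 and 96 h, with change from the period baseline already defined in SAP 11.1.1;
- list all laboratory values by subject and scheduled time, as Protocol 9.1 states, with out-of-range values flagged.

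Align the table shells with this text. If they already contain these tables, only the SAP wording needs to change.

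If the sponsor intends to omit the summaries, correct SAP 13 to declare the departure from Protocol 9.1 and 9.5. That corrects the record but does not restore the description of laboratory levels, so adding the tables is the better course.

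The cost is SAP wording, routine programming and a few more tables from data already collected. No protocol amendment, extra sample or extra subject is needed.
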